### **15.1 Adverse Event (AE)**

All AEs must be recorded on the AE CRF. AEs should be followed to resolution or stabilization (if possible), and reported as serious adverse events (SAEs) if they become serious.

LSRs that have been reported in subjects treated with CB-03-01 creams (0.1%-1% concentration) include (with decreasing frequency) erythema, pruritus, scaling/dryness, skin atrophy, striae rubrae, stinging/burning, edema, and telangiectasia; however most LSRs were typically of minimal to mild severity. No subjects discontinued treatment due to these LSRs.

AEs that have been reported in subjects treated with CB-03-01 creams (0.1-1% concentration) were minimal, typically mild in severity, and most were recovered/resolved without sequelae at the end of the study. Only two AEs in one (1) subject were judged as probably or possibly related to treatment; both of these treatment-related AEs (burning and cold at application site) were mild in severity. Two SAEs have been reported to date; both were not related to treatment and were resolved at the end of the study. In addition, one subject discontinued early from the study due to an AE (urinary tract infection), which was not related to treatment.

The investigator will instruct the subject to report any AEs that may occur during the study. At each visit, the investigator should ask the subject, in non-directive fashion, about any change in the subject’s overall condition since the previous visit.

The severity of each AE, as judged by the investigator, will be recorded on the appropriate AE CRF and will be graded according to the following scale:

**Mild** - The AE is transient and easily tolerated by the subject.

**Moderate** - The AE causes the subject discomfort and interrupts the subject's usual activities.

**Severe** - The AE causes considerable interference with the subject's usual activities, and may be incapacitating or life-threatening.

The investigator must determine the relationship of the AE to the test article according to the following categories:

**Definite** - An event that follows a reasonable temporal sequence from administration of the test article; that follows a known or expected response pattern to the test article; and that is confirmed by improvement on stopping or reducing the dosage, and reappearance of the event on repeated exposure (re-challenge).

**Probable** - An event that follows a reasonable temporal sequence from administration of the test article; that follows a known or expected response pattern to the test article; and that is confirmed by improvement on stopping or reducing the dosage of the test article; and that is unlikely to have been caused by concurrent/underlying illness or other drugs, procedures, or other causes.

**Possible** - An event that follows a reasonable temporal sequence from administration of the test article; that follows a known or expected response pattern to the test article; but may have been caused by concurrent/underlying illness, other drug, procedure, or other causes.

**Unlikely** - An event that does not follow a reasonable temporal sequence from administration of the test article; that does not follow a known or expected response pattern to the test article, or most likely was caused by concurrent/underlying illness, other drug, procedure, or other causes, because of their known effects.

**Not Related** - An event almost certainly caused by concurrent/underlying illness, other drug, procedure, or other causes.

The investigator should categorize the outcome of the AE according to the following categories:

**Fatal** - Termination of life as a result of an AE.

**Not Recovered/Not Resolved** - AE has not improved or the subject has not recuperated.

**Recovered/Resolved** - AE has improved or the subject has recuperated.

**Recovered/Resolved with Sequelae** - subject recuperated but retained the pathological conditions resulting from the prior disease or injury.

**Recovering/Resolving** - AE is improving or the subject is recuperating.

**Unknown** - Not known, not observed, not recorded or subject refused.

An **adverse reaction** is any AE caused by a drug. Adverse reactions are a subset of all suspected adverse reactions for which there is reason to conclude that the drug caused the event. For the purposes of prescription drug labeling, the term adverse reaction means an undesirable effect, reasonably associated with the use of a drug that may occur as part of its pharmacological action or may be unpredictable in its occurrence.

A **suspected adverse reaction** is any AE for which there is a reasonable possibility that the drug caused the event.

For the purposes of IND safety reporting, “reasonable possibility” means there is evidence to suggest a causal relationship between the drug and the AE. A suspected adverse reaction implies a lesser degree of certainty about causality than adverse reaction, which means any AE caused by a drug.

An AE or suspected adverse reaction is considered “unexpected” if it is not listed in the investigator brochure or is not listed at the specificity or severity that has been observed; or, if an investigator brochure is not required or available, is not consistent with the risk information described in the general investigational plan or elsewhere in the current application. For example, under this definition, hepatic necrosis would be unexpected (by virtue of greater severity) if the investigator brochure referred only to elevated hepatic enzymes or hepatitis. Similarly, cerebral thromboembolism and cerebral vasculitis would be unexpected (by virtue of greater specificity) if the investigator brochure listed only cerebral vascular accidents. "Unexpected," as used in this definition, also refers to AEs or suspected adverse reactions that are mentioned in the investigator brochure as occurring with a class of drugs or as anticipated from the pharmacological properties of the drug, but are not specifically mentioned as occurring with the particular drug under investigation.

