## 8. DOSE LIMITING TOXICITY (DLT) AND “STOPPING RULES”

The Medical Monitor will consider Dose Limiting Toxicity (DLT) when reviewing the safety data. A DLT is defined as a systemic Grade 2 or higher (CTCAE, Version 4.0) adverse event (AE) for which there is no clear alternative explanation of the cause of the AE. Non-systemic (local) AEs Grade 3 or higher for which there is no clear alternative explanation of the cause of the AE will also be considered DLTs. If more than 3 subjects within the study exhibit a DLT, enrollment will be stopped. Any subject who experiences a DLT, as described above, must discontinue treatment and be scheduled for a final visit. Any DLTs that are Grade 2 or greater systemic AEs with documented worsening from Baseline must be reported by the investigator immediately.

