### 14.2 Subject Discontinuation

A subject may be withdrawn from the study prior to completion for any of the following reasons:

- Whenever the subject or the subject's parent/guardian decides it is in the subject's best interest to withdraw. NOTE: if the subject decides to withdraw from the study due to an AE then it should be classified as withdrawal due to an AE.
- Whenever the investigator decides it is in the subject's best interest to be withdrawn
- AEs
- Progressive disease
- Noncompliance with study drug
- Protocol deviation
- Pregnancy (if applicable)
- Lost to follow-up
- Study terminated by Sponsor
- Death

If a subject withdraws from the study prematurely for any reason, every attempt should be made to complete the EOS procedures prior to discharging the subject from the study. If a subject withdraws prematurely during the treatment period for any reason, the Visit 4 procedures (minus the PK blood draw) will be completed. Subjects who withdraw prematurely will be replaced until at least 20 subjects with both Screening and Day 14 serum cortisol data (pre- and post-cosyntropin stimulation) have completed the study without any significant protocol violations (i.e., evaluable subjects). When a subject is withdrawn from the study for a treatment-related AE (i.e., possibly, probably or definitely related as defined in [Section 15.1](#)), when possible, the subject should be followed until resolution of the AE.

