7.8.1 Adverse Events

Adverse events (AEs) will be coded using the Medical Dictionary for Regulatory Activities (MedDRA) version 19.1. Verbatim terms will be mapped into a MedDRA system organ class (SOC) and preferred term (PT). For all AE summaries, if a subject has more than one AE within a PT, the subject is counted once in that PT. If a subject has more than one AE within a SOC, the subject is similarly counted once in that SOC.

The number and percentage of unique subjects reporting any local and systemic treatment-emergent AE will be summarized by SOC and PT. The number and percent of unique subjects reporting any local and systemic TEAE will also be summarized by SOC, PT, and maximum severity (mild, moderate, severe) and closest relationship to test article (not related, unlikely, possibly, probably related).

Serious AEs and DLTs, if any, will be listed separately.

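### The adverse event causality scale gives a well-timed but novel reaction no treatment-related category, which biases the relationship table toward fewer related events

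*Protocol*

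**What the plan says.** Protocol 15.1 tells the investigator to assign one of five relationship categories.

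- **Definite** needs suitable timing and an event "that follows a known or expected response pattern to the test article; and that is confirmed by improvement on stopping or reducing the dosage", plus recurrence on re-challenge.
- **Probable** carries the same timing, pattern and improvement conditions and adds an event "that is unlikely to have been caused by concurrent/underlying illness or other drugs, procedures, or other causes".
- **Possible** needs suitable timing and an event "that follows a known or expected response pattern to the test article; but may have been caused by concurrent/underlying illness" or another factor.
- **Unlikely** covers an event with poor timing, and one "that does not follow a known or expected response pattern to the test article, or most likely was caused by concurrent/underlying illness" or another factor.
- **Not Related** needs an almost certain other cause.

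Protocol 14.2 and 15 treat the first three categories, and only those, as treatment-related. Protocol 14.2 reads: "When a subject is withdrawn from the study for a treatment-related AE (i.e., possibly, probably or definitely related".

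Two other causality concepts in the protocol have no pattern condition. In 15.1 a suspected adverse reaction "is any AE for which there is a reasonable possibility that the drug caused the event", and the same section recognises that such a reaction can be unexpected. In Section 8 a DLT is a systemic event of Grade 2 or higher, or a local event of Grade 3 or higher, "for which there is no clear alternative explanation of the cause of the AE".

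SAP 6.3 repeats the five labels without defining them. SAP 7.8.1 summarises treatment-emergent AEs by "closest relationship to test article (not related, unlikely, possibly, probably related", which becomes Table 14.3.3.3.

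**The concern.** The study has no control arm and enrols children aged 9 to under 12. The earlier HPA/PK study described in Protocol 2 enrolled adolescents and adults. Without a comparator, the investigator's attribution is the main way for the report to separate drug effects from background events. A scale that makes a familiar pattern a condition of relatedness cannot record a new drug effect as related. The error runs one way, toward fewer related events, and it affects novel reactions in an age group not covered by that earlier study.

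The scale also sits badly with the rest of the protocol, which accepts that a drug can cause an unexpected reaction. An event could be counted as a DLT because no other cause is apparent and still be tabulated as unlikely related.

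**Working it through.** The plan gives no figure to reproduce. The check is on the logic of the definitions, followed by an illustration of size.

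**Step 1. The conditions side by side (Protocol 15.1).**

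| Category | Timing | Known or expected pattern | Improves on stopping | Re-challenge | Other cause |
|---|---|---|---|---|---|
| Definite | required | required | required | required | not mentioned |
| Probable | required | required | required | not mentioned | unlikely |
| Possible | required | required | not mentioned | not mentioned | may exist |
| Unlikely | absent (first limb) | absent (second limb) | not mentioned | not mentioned | most likely (third limb) |
| Not Related | not mentioned | not mentioned | not mentioned | not mentioned | almost certain |

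The text does not say whether the first two limbs of Unlikely are joined by *and* or by *or*.

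**Step 2. Events without a known pattern.** Take timing (2 levels), improvement on stopping (2), re-challenge (2) and other cause (4: none, may, most likely, almost certain). This gives 2 × 2 × 2 × 4 = 32 combinations. Because the pattern is a joint condition of all three related categories, 0 of 32 reach Definite, Probable or Possible. The reading of Unlikely makes no difference to that result.

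**Step 3. The case of interest: good timing, no known pattern, no other cause.** Four combinations remain (improvement yes/no × re-challenge yes/no).

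- If the first two limbs of Unlikely must both hold, all four fit no category.
- If the limbs are alternatives, all four are Unlikely.
- Not Related never applies, because it needs another cause.
- Positive re-challenge changes nothing.

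**Step 4. The same event under the other definitions.** Good timing and no other cause can support a reasonable possibility that the drug caused the event, so it can be a suspected adverse reaction. If it also reaches the required grade, it meets the DLT definition. Neither definition asks about pattern.

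**Step 5. Illustrative size.** The denominator is 24, the approximate enrolment in the protocol synopsis. The event counts are invented for illustration. Intervals are Clopper-Pearson 95%.

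- No event scored related: 0/24 = 0%. The upper limit is 1 − 0.025^(1/24) = 14.2%.
- One such event scored related: 1/24 = 4.2% (0.1 to 21.1%).
- Four such events scored related: 4/24 = 16.7% (4.7 to 37.4%). Four subjects with DLTs exceed the limit of three in Section 8, yet the relationship table could still show 0/24 related. The denominator of 24 assumes that all were dosed before enrolment stopped.

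**Step 6. A neighbouring gap.** A well-timed event of known pattern, with no other cause and no improvement on stopping, also fits no category. Possible presupposes another potential cause, and Probable and Definite need improvement.

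**The case against.** The strongest reply is that little depends on this scale, and most of that stands.

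- All serious AEs are reported whatever their relationship, with a separate reasonable-possibility assessment (Protocol 15.2).
- The DLT rule works without it (Protocol 8, SAP 7.11).
- An abnormal end-of-study cosyntropin result is attributed to the cream by rule (Protocol 13.5, SAP 6.5).
- All treatment-emergent AEs are tabulated regardless of relationship (Table 14.3.3.1), serious AEs and DLTs are listed separately, and an AE listing is planned.
- With about 24 children, each event can be read individually. No hypothesis or decision rests on a related-AE rate, and no interval for one is planned.

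Three stronger readings are tempting, and the documents do not support them.

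1. A reader might infer from Protocol 14.2 that a child withdrawn with such an event loses follow-up. The opening of 15.1 asks for AEs in general to be followed to resolution or stabilisation where possible, and Section 15 provides for follow-up of events that interrupt or end treatment.
2. A reader might infer that the known pattern is almost empty, because 15.1 reports only two related AEs, in one subject. The same section lists eight local skin reactions seen in treated subjects, and Protocol 2 reports laboratory adrenal suppression in 1/20 adults and 2/22 adolescents, 3 of 42 in all.
3. A reader might call the definitions flatly contradictory. They serve different purposes, and one event can carry both a DLT flag and a relationship score. They are poorly aligned, but not logically incompatible.

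It can also be said that *expected* may be read broadly enough to take in pharmacologically plausible effects. That is possible, but the phrase is undefined for this scale. The nearest definition, of unexpected events in 15.1, counts as unexpected an effect anticipated from pharmacology but not specifically mentioned for this drug. That definition is limited to its own use, so it settles nothing either way. Investigators at about six sites in two countries could score the same event differently.

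**Conclusion.** The gap is real on the wording of Protocol 15.1, and the SAP does not close it. A well-timed novel AE without another cause cannot be scored treatment-related. It becomes Unlikely or has no category.

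The consequence is limited to Table 14.3.3.3 and to any statement of related-AE frequency, where the bias is toward fewer related events for novel toxicity. The documents give no expected frequency for such events, so the size cannot be estimated. The shift from 0/24 to 1/24 shows only what a single event would do.

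The conclusion assumes that investigators apply the definitions literally and that no guidance outside the two documents widens the meaning of *expected*. It is a modest point, worth correcting because the correction is cheap.

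**What to change.** **Protocol 15.1.** Reword Possible as suitable timing together with a reasonable possibility that the test article caused the event, whether or not it follows a known or expected pattern and whether or not another cause is also possible. Remove absence of a known pattern as a sufficient feature of Unlikely, and state how its remaining conditions are joined. The new wording of Possible can also take the events in Step 6.

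**SAP 7.8.1.** Add one sentence: any DLT scored unlikely or not related is flagged in the DLT listing. The investigator's recorded score should stand. Re-labelling every DLT as at least possibly related would expose the same conflict, but by overriding an assessment that the protocol assigns to the investigator. In the same edit, add the definitely related category, which SAP 6.3 lists and 7.8.1 omits.

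**Cost.** Two reworded definitions, matching case report form guidance and a small SAP edit. The five labels stay the same. The related-AE count may come out slightly higher than under the present wording.

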## 15.2 Serious Adverse Event (SAE)

An event that is serious must be recorded on the AE CRF and on the CRO SAE Report Form, and requires expeditious handling to comply with regulatory requirements.

An AE or suspected adverse reaction is considered “serious” if, in the opinion of either the investigator or Sponsor, it results in any of the following outcomes:

- Death.
- Life-threatening event.
- Inpatient hospitalization or prolongation of existing hospitalization.
- Persistent or significant incapacity or substantial disruption of the ability to conduct normal life functions.
- Congenital anomaly/birth defect.
- Is an important medical event - defined as a medical event(s) that may not result in death, be life-threatening, or require hospitalization but, based upon appropriate medical judgment, may jeopardize the patient/subject and may require medical or surgical intervention to prevent one of the outcomes listed in the definition above. Examples of such medical events include allergic bronchospasm requiring intensive treatment in an emergency room or at home, blood dyscrasias or convulsions that do not result in inpatient hospitalization, or the development of drug dependency or drug abuse.

Events NOT considered to be serious AEs are:

- Hospitalizations for the treatment, which was elective or pre-planned, of a pre-existing condition that did not worsen, and
- Treatment on an emergency, outpatient basis, for an event not fulfilling any of the definitions of “serious” given above and not resulting in hospital admission.

AEs classified as “serious” by either the investigator or the Sponsor require expeditious handling and reporting to the CRO to comply with regulatory requirements. **All serious AEs, whether related or unrelated to test article, must be immediately reported by telephone to the Medical Monitor and, in the event that he/she is unavailable, to the Project Manager listed on the first page of the protocol.** Written notification of all SAEs should be sent to the Project Manager by email or confirmed facsimile transmission. These include those SAEs listed in the protocol or investigator brochure and must include an assessment of whether there is a reasonable possibility that the drug caused the event.

Study endpoints that are SAEs (e.g., all-cause mortality) must be reported in accordance with the protocol unless there is evidence suggesting a causal relationship between the drug and the event (e.g., death from anaphylaxis). In this case, the investigator must immediately report the event to the Sponsor. In addition, such information should also be provided to the site’s respective IRB/IEC per their governing guidelines for SAE reporting.

If only limited information is initially available, follow-up reports are required. Should the investigator become aware of a SAE (regardless of its relationship to test article) that occurs within 30 days after stopping the test article, the SAE must be reported in accordance with procedures specified in this protocol. In the event of death, if an autopsy is performed, a copy of the report should be sent to the CRO, if available.

As required, the CRO will notify participating investigators of all suspected adverse reactions that are serious and unexpected. This notification will be in the form of an IND safety report of potential serious risks as soon as possible but no later than 15 calendar days after the Sponsor determines that the information is “reportable” according to the criteria listed in 21 CFR Section 312.32. These are:

- i) Serious and unexpected suspected adverse reactions,
- ii) Findings from other studies including epidemiological studies, pooled analyses or other clinical studies that suggest a significant risk in humans exposed to the test articles,
- iii) Findings from animal or in vitro tests that suggest a significant risk to humans exposed to the test articles, or reports of significant organ toxicity at or near the expected human exposure, and
- iv) Clinically important increases in the rate of occurrence of serious suspected adverse reactions.

Upon receiving such notices, the investigator must review and retain the notice with the Investigator Brochure and immediately submit a copy of this information to the responsible IRB/IEC according to local regulations. The investigator and IRB/IEC will determine if the informed consent/assent requires revision. The investigator should also comply with the IRB/IEC procedures for reporting any other safety information. Where required, submission of safety updates by the investigator to Health Authorities should be handled according to local regulations.

### 15.3 Laboratory Test Abnormalities

In addition to being recorded on the appropriate laboratory test results CRF, or being electronically submitted from a central laboratory, any clinically significant laboratory test result that meets the criteria for an AE (see [Section 15](#)) or SAE (see [Section 15.2](#)) must also be recorded on the AE CRF. SAEs must be reported to the Sponsor and IRB/IEC as per [Section 15.2](#). In these cases, the CRO will typically require additional information about the clinically significant abnormality, including information regarding relationship to test article or other causes, any action taken, and resolution. Other laboratory test abnormalities will be addressed by the investigator on the actual laboratory test reports, and on the associated laboratory test results CRF.

